6.2.2. Exclusion Criteria

A patient who meets any of the following criteria will be excluded from the study:

1. LDL-C level <70 mg/dL (1.81 mmol/L) at the screening visit.
2. Background medical LMT (if applicable) that has not been stable for at least 4 weeks (6 weeks for fibrates, 8 weeks for PCSK9 inhibitor antibodies, 12 weeks for MTD of lomitapide, 24 weeks for mipomersen) before the screening visit
3. Lipid-apheresis schedule (every 7 or 14 days)/apheresis settings (if applicable) that have not been stable for at least 8 weeks before the screening visit or an apheresis schedule that is not anticipated to be stable over the next 48 weeks. Plasma exchange is excluded.

4. Use of nutraceuticals or over-the-counter therapies known to affect lipids, at a dose/amount that has not been stable for at least 4 weeks prior to the screening visit or between the screening and randomization visits
5. Presence of any clinically significant uncontrolled endocrine disease known to influence serum lipids or lipoproteins
Note: patients on thyroid replacement therapy can be included if the dosage of replacement therapy has been stable for at least 12 weeks prior to screening and the thyroid stimulating hormone (TSH) level is within the normal range of the central laboratory at the screening visit.
6. Newly diagnosed (within 3 months prior to randomization visit [week 0/day 1]) diabetes mellitus or poorly controlled (HbA1c >9%) diabetes
7. Unstable weight (variation >5 kg) within 2 months prior to the screening visit (week -2)
8. Initiation of a new diet or major change to a previous diet within 4 weeks prior to screening
9. Use of systemic corticosteroids, unless used as replacement therapy for pituitary/adrenal disease with a stable regimen for at least 6 weeks prior to screening
Note: topical, intra-articular, nasal, inhaled and ophthalmic steroid therapies are not considered as 'systemic' and are allowed
10. Use of estrogen or testosterone therapy unless the regimen has been stable 6 weeks prior to the screening visit and no plans to change the regimen during the study
11. Systolic blood pressure >160 mmHg or diastolic blood pressure >100 mmHg at the screening visit or time of randomization (week 0/day 1)

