4.8.1.2. Adverse Events of Special Interest

Adverse events of special interest (AESI) are AEs (serious or non-serious) required to be monitored, documented, and managed in a pre-specified manner. AESIs will be recorded on the adverse event e-CRF using dedicated tick boxes, and/or identified using standard MedDRA queries (SMQ), company MedDRA queries (CMQ), and/or applicable laboratory assessments. Appendix 10.3 contains the definitions used to identify AESIs:

The AESIs include:

- Anaphylactic reactions (e-CRF)
- General allergic events (SMQ)
- Infusion reactions (e-CRF)
- Hepatic Disorder (SMQ, lab data)
- Pregnancy (e-CRF)
- Symptomatic overdose with investigational medicinal product (e-CRF)
- Neurocognitive events (CMQ)
- Neurologic events (e-CRF)
- New onset of diabetes (NOD) (lab data, HLT, concomitant medications) for patients without diabetes mellitus at baseline
- Diabetic complication (CMQ, concomitant medications) for patients with diabetes mellitus at baseline
- Pancreatitis (e-CRF)

- Cataracts (MedDRA HLT)
- Immune complex diseases (SMQ)
- Muscle events/CK elevation (MedDRA SOC, SMQ, lab data)

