- Analyses performed according to diabetes status will be done considering diabetic patients as patients with either type 1 or type 2 diabetes in the medical history e-CRF page (regardless of the ongoing status).

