
New onset of diabetes (NOD) for patients without diabetes mellitus at baseline
	
No
	
No medical history of diabetes as specified in Cardiovascular History and Cardiovascular Risk Factors and Medical History CRF pages AND one of the following:
 
Lab criteria: At least 2 values of HbA1c $\geq 6.5\%$ during the TEAE period. NOTE: For patients with only a single measurement available during the TEAE period, a single value $\geq 6.5\%$ will be considered and qualify the patient as NOD by default. For patients with several HbA1c measurements but only with the last one $\geq 6.5\%$, this single value $\geq 6.5\%$ will be considered and qualify the patient as NOD by default.
 
OR
 
Lab criteria: At least 2 values of fasting glucose ≥ 126 mg/dL (7.0 mmol/L). NOTE: For patients with only a single measurement available during the TEAE period, a single value ≥ 126 mg/dL (7.0 mmol/L) will NOT be considered and will NOT qualify the patient as NOD. For patients with several fasting glucose measurements but only with the last one ≥ 126 mg/dL (7.0 mmol/L), this single value ≥ 126 mg/dL (7.0 mmol/L) will NOT be considered and will NOT qualify the patient as NOD.
 
OR
 
HLT Diabetes mellitus (including subtypes)
 
OR
 
Initiation of any new concomitant medication for hyperglycemia during the treatment period

Diabetic complication for patients
	
No
	
For patients with medical history of diabetes as specified in Cardiovascular History and Cardiovascular Risk

with diabetes mellitus at baseline		
Factors and Medical History CRF pages, each of the following criteria will be considered, respectively:
 
 • Diabetes mellitus or diabetic complication TEAEs using HLT Diabetic complications, HLT Diabetes mellitus (incl subtypes), and PTs Blood glucose increases, Glycosylated haemoglobin increased, Hyperglycaemia, Hyperglycaemic unconsciousness, and Hyperglycaemic seizure • Changes in diabetic medication dosage (specifically increases in dosage) or initiation of additional diabetic medication
Pancreatitis	Yes	No
Cataracts	No	HLT Cataract conditions
Immune complex diseases	No	
SMQ (Narrow) Systemic lupus erythematosus
 
SMQ (Narrow) Vasculitis
 
SMQ (Narrow) Guillain-Barre syndrome

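### The new-onset diabetes rule checks for baseline diabetes by CRF history only, so a patient with no recorded history but baseline HbA1c already at or above 6.5% can be counted as a new case

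*SAP*

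**What the plan says.** SAP 4.8.1.2 lists the event as "New onset of diabetes (NOD) (lab data, HLT, concomitant medications) for patients without diabetes mellitus at baseline". Appendix 10.3 turns the baseline restriction into one condition, "No medical history of diabetes as specified in Cardiovascular History and Cardiovascular Risk Factors and Medical History CRF pages", and then requires any one of four criteria:

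- HbA1c. The rule begins "Lab criteria: At least 2 values of HbA1c" and sets the cut-off at 6.5% or above within the treatment-emergent (TEAE) period. One value is enough if it is the only measurement or the last one. The default clause begins "For patients with only a single measurement available during the TEAE period, a single value".
- Fasting glucose. The rule begins "Lab criteria: At least 2 values of fasting glucose" and sets the cut-off at 126 mg/dL or above. Here an only or last raised value does not qualify.
- A diabetes adverse event, identified by MedDRA high-level term.
- A newly started medication for hyperglycemia.

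None of the four refers to a baseline value. SAP 5.8 sets the general rule the same way: diabetic patients are "patients with either type 1 or type 2 diabetes in the medical history e-CRF page (regardless of the ongoing status"). Protocol 9.4.3 gives the same two laboratory criteria with neither a history nor a baseline condition.

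**The concern.** A new-onset rule has to separate patients who develop the condition from those who arrive with it. History does that only for diabetes that has been diagnosed and recorded. For a patient whose HbA1c was already raised before the first dose, the laboratory criteria ask whether it is still raised, not whether anything has changed.

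At stake is a small safety count. A pre-existing condition would appear as a treatment-emergent event of special interest, in arms where one patient visibly moves the percentage. The same patient would be left out of the companion row for diabetic complications, which is also restricted by CRF history. Randomization balances this between arms only on average.

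**Working it through.** The plan states no figure to reproduce, so the check follows a patient through the rule.

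**Can such a patient enter?** Exclusion criterion 6 in Protocol 6.2.2 removes "Newly diagnosed (within 3 months prior to randomization visit [week 0/day 1]) diabetes mellitus or poorly controlled (HbA1c >9%) diabetes". It does not clearly remove someone with undiagnosed diabetes and HbA1c between 6.5% and 9%. HbA1c does not appear in the run-in and screening schedules (Protocol Tables 1 and 2). It is first drawn on day 1 and then at weeks 12, 24, 36 and 48 (Table 3). Medical history is taken at screening, before the day 1 result exists.

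**Does the rule then count the patient?** The table applies the HbA1c criterion of Appendix 10.3 to example patients with no diabetes history, first as written and then with a condition that baseline HbA1c be below 6.5%.

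| Baseline HbA1c (%) | On-study values in the period (%) | As written | With baseline condition |
|---|---|---|---|
| 6.8 | 6.8, 6.8 | new-onset | not |
| 6.8 | 6.7 only | new-onset | not |
| 6.8 | 6.4, 6.6 | new-onset | not |
| 8.9 | 8.8, 8.9 | new-onset | not |
| 6.8 | 6.6, 6.4 | not | not |
| 5.6 | 6.6, 6.7 | new-onset | new-onset |
| 5.6 | 5.6, 5.7 | not | not |

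The first four rows are patients already at or above the cut-off at baseline. The sixth is a true incident case, and the added condition keeps it. The glucose criterion has the same gap on reading; it was not run on examples.

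**How many values are needed in the double-blind period?** For patients going on to open label, that TEAE period ends the day before the first open-label dose (SAP 4.8.1). Week 24 blood is drawn before that dose, normally on the same day. Week 12 is then typically the only scheduled HbA1c inside the period, and by the default clause one value at or above 6.5% suffices.

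**Size.** With the planned arms of 38 and 19 (SAP 2.2), one misclassified patient adds 1/38 = 2.6 percentage points in evinacumab or 1/19 = 5.3 in placebo.

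**Frequency.** The documents give no prevalence of undiagnosed diabetes at baseline. Purely as assumed values, the expected number is 57p and the chance of at least one is 1 − (1 − p)^57:

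- p = 1%: 0.6 patients expected; chance 44%
- p = 2%: 1.1 patients expected; chance 68%
- p = 5%: 2.9 patients expected; chance 95%

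**Is the remedy consistent with the SAP?** Appendix 10.4 already requires a baseline at or below the same cut-off for its ALT, AST, alkaline phosphatase, total bilirubin and CPK criteria. SAP 4.1 tabulates baseline HbA1c with a category at 6.5% and above. One report could therefore show a patient in that category and also as new-onset.

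**The case against.** A reader might infer that every patient with a raised baseline HbA1c will be counted. The documents do not support that, because an on-study criterion must still be met. A patient at 6.8% who then records 6.6% and 6.4% in the period is not new-onset by HbA1c.

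Screening is not blind to diabetes either. Blood chemistry at screening includes glucose, lipid samples at clinic visits are fasting, and the investigator must review all laboratory values (Protocol 8.2.2 and the Laboratory Testing section). A patient diagnosed from that result would fall under exclusion criterion 6. This narrows the route, most clearly for raised glucose. It does not catch a patient whose HbA1c is raised while fasting glucose is below 126 mg/dL.

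The results are partly self-correcting. Baseline HbA1c is tabulated by arm and HbA1c is summarized by visit, so a reader could see that such patients exist. The tables would not show which new-onset cases they are. An inclusive safety rule also fits the SAP's conservative approach to calling events treatment-emergent. That approach in SAP 5.8.1, however, concerns incomplete onset dates and does not justify counting a condition measured before dosing.

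The objection with most force concerns the remedy. A baseline laboratory condition placed on the whole definition would also discard patients with a later diabetes adverse event or newly started medication. It would let a single baseline glucose establish diabetes, although the SAP does not accept a single on-study glucose as proof. The condition must therefore be confined to the laboratory criteria.

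**Conclusion.** The point stands in limited form. The stated population is "for patients without diabetes mellitus at baseline", yet the rule tests only recorded history, so a patient with no history and a baseline HbA1c at or above 6.5% can be counted as new-onset on unchanged values. The row label does not rescue the rule, because the text beneath it and SAP 5.8 both define diabetic status by history.

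The size is that of one misclassified patient against the planned arm sizes. Whether any such patient enrolls is unknown, and the assumed prevalences are illustrations only. SAP 5.8 specifies descriptive safety summaries without formal testing. It would be wrong to infer a predictable bias against either arm or any effect on the efficacy conclusions. This is a minor correction, worth making because it is cheap.

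**What to change.** In Appendix 10.3, add a baseline condition to the two laboratory criteria and to nothing else:

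- The HbA1c criterion counts only if baseline HbA1c is below 6.5%.
- The fasting-glucose criterion counts only if baseline HbA1c is below 6.5% and baseline fasting glucose, when available, is below 126 mg/dL.

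Leave the diabetes adverse-event and new-medication criteria unchanged. A raised baseline glucose then switches off only the glucose route and does not by itself label the patient diabetic. Flag patients with no history but baseline values at or above either cut-off and list them separately by arm, including any who qualify through the two unchanged criteria.

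Baseline HbA1c and chemistry are already collected on day 1. The cost is a few extra lines of programming and a small departure from the laboratory wording of Protocol 9.4.3, to be recorded in SAP 1.2.4. SAP section 1 allows revision on blinded review before the first-step database lock. One loss should be accepted openly: a patient whose already raised HbA1c climbs further on study no longer counts by the laboratory criteria. The separate listing keeps that patient in view.

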10.4. Criteria for Potentially Clinically Significant Values (PCSV)

Parameter	PCSV
Clinical chemistry	
ALT	By distribution analysis: >2 ULN and baseline \leq 2 ULN >3 ULN and baseline \leq 3 ULN >5 ULN and baseline \leq 5 ULN >10 ULN and baseline \leq 10 ULN >20 ULN and baseline \leq 20 ULN
AST	By distribution analysis: >2 ULN and baseline \leq 2 ULN >3 ULN and baseline \leq 3 ULN >5 ULN and baseline \leq 5 ULN >10 ULN and baseline \leq 10 ULN >20 ULN and baseline \leq 20 ULN
Alkaline Phosphatase	> 1.5 ULN and baseline \leq 1.5 ULN
Total Bilirubin	> 1.5 ULN and baseline \leq 1.5 ULN > 2 ULN and baseline \leq 2 ULN
Conjugated bilirubin	> 35% total bilirubin (when total bilirubin >1.5 ULN)
ALT and Total Bilirubin	ALT > 3 ULN and Total Bilirubin > 2 ULN and baseline ALT \leq 3 ULN or Total bilirubin \leq 2 ULN
CPK	> 3 ULN and \leq 5 ULN and baseline \leq 3ULN >5 ULN and \leq 10 ULN and baseline \leq 5 ULN >10 ULN and baseline \leq 10 ULN
Creatinine	\geq 150 μ mol/L (adults) \geq 30% from baseline \geq 100% from baseline
CLcr (mL/min) (Estimated creatinine clearance based on the Cockcroft-Gault equation)	\geq 15 - <30 (severe decrease in GFR) \geq 30 - < 60 (moderate decrease in GFR) \geq 60 - <90 (mild decrease in GFR) \geq 90 (normal GFR)
eGFR (mL/min/1.73m ²) (Estimate of GFR based on an MDRD equation)	\geq 15 - <30 (severe decrease in GFR) \geq 30 - < 60 (moderate decrease in GFR) \geq 60 - <90 (mild decrease in GFR) \geq 90 (normal GFR)

Parameter	PCSV
Uric Acid Hyperuricemia: Hypouricemia:	>408 µmol/L <120 µmol/L
Blood Urea Nitrogen	≥17 mmol/L
Chloride	<80 mmol/L >115 mmol/L
Sodium	≤129 mmol/L ≥ 160 mmol/L
Potassium	< 3 mmol/L ≥ 5.5 mmol/L
Glucose Hypoglycaemia Hyperglycaemia	≤ 3.9 mmol/L and < LLN ≥ 7 mmol/L (fasted); ≥ 11.1 mmol/L (unfasted)
HbA1c	>8%
Albumin	≤25 g/L
Hs-CRP	> 2 ULN or >10 mg/L, if ULN not provided
Hematology	
WBC	< 3.0 Giga/L (3000/ mm ³) (Non-Black) < 2.0 Giga/L (2000/ mm ³) (Black) ≥16.0 Giga/L (16000/ mm ³)
Lymphocytes	>4.0 Giga/L
Neutrophils	< 1.5 Giga/L (1500/ mm ³) (Non-Black) < 1.0 Giga/L (1000/ mm ³) (Black)
Monocytes	>0.7 Giga/L
Eosinophils	> 0.5 Giga/L (500/ mm ³) or > ULN if ULN ≥ 0.5 Giga/L
Hemoglobin	≤115 g/L (Male); ≤95 g/L (Female) ≥185 g/L (Male); ≥165 g/L (Female) Decrease from Baseline ≥15 g/L Decrease from Baseline ≥20 g/L
Hematocrit	≤0.37 v/v (Male) ; ≤0.32 v/v (Female) ≥0.55 v/v (Male) ; ≥0.5 v/v (Female)
RBC	≥6 Tera/L

Parameter	PCSV
Platelets	< 100 Giga/L (100 000/mm ³) ≥700 Giga/L (700000/mm ³)
Urinalysis	
pH	≤4.6 ≥8
Vital signs	
HR	≤ 50 bpm and decrease from baseline ≥ 20 bpm ≥ 120 bpm and increase from baseline ≥ 20 bpm
SBP	≤ 95 mmHg and decrease from baseline ≥ 20 mmHg ≥ 160 mmHg and increase from baseline ≥ 20 mmHg
DBP	Young and elderly patients ≤ 45 mmHg and decrease from baseline ≥ 10 mmHg ≥ 110 mmHg and increase from baseline ≥ 10 mmHg
Orthostatic Hypotension	SBP St – Su ≤ - 20 mmHg DBP St – Su ≤ - 10 mmHg
Weight	≥5% increase versus baseline ≥5% decrease versus baseline
ECG parameters	
HR	≤ 50 bpm and decrease from baseline ≥ 20 bpm ≥ 120 bpm and increase from baseline ≥ 20 bpm
PR	≥220 ms and increase from baseline ≥20 ms
QRS	≥ 120 ms
QTc Borderline Prolonged* Additional	Absolute values (ms) Borderline 431-450 ms (Male) 451-470 ms (Female) Prolonged* > 450 ms (Male) > 470 ms (Female) QTc ≥500 ms Increase versus baseline (Males and Females) Borderline Δ 30-60 ms Prolonged * Δ > 60 ms

10.5. EQ-5D Utility Score Algorithm

EQ-5D Utility Score Algorithm

Algorithm: UK based

```
/*=====*/  
;  
  
/* Aim : Derive the EQ5-D index (utility)  
*/;  
  
/* Source for the algorithm : scoring EQ-5D health states (Rosalind Rabin  
*/;  
  
/* (cf. G:\_HE\PRO questionnaire\EQ5D\scoring\YorkTariffx.doc)  
*/;  
  
/* Note : UK based population (Dolan, 1997)  
*/;  
  
/*=====*/  
;
```

Answer to questions in numeric format, from 1 (no problem) to 3 (severe problem); Q1 (mobility), Q2 (self-care), Q3 (usual activities), Q4 (pain/discomfort), Q5 (anxiety/depression)

Result of the algorithm: Utility (EQ-5D utility score).

If at least one of the answer to questions is missing then the utility score is missing.

Start with Utility =1 and apply the following sequential algorithm.

*****Mobility*****

if Q1=2 then Utility = Utility - **0.069**

if Q1=3 then Utility = Utility - **0.314**

*****Self-care*****

if Q2=2 then Utility = Utility - **0.104**

if Q2=3 then Utility = Utility - **0.214**

*****Usual activities*****

if Q3=2 then Utility = Utility - **0.036**

if Q3=3 then Utility = Utility - **0.094**

*****Pain/discomfort*****

if Q4=2 then Utility = Utility - **0.123**
 if Q4=3 then Utility = Utility - **0.386**

*****Anxiety/depression*****

if Q5=2 then Utility = Utility - **0.071**
 if Q5=3 then Utility = Utility - **0.236**

if (Q1 ≠ 1 or Q2 ≠ 1 or Q3 ≠ 1 or Q4 ≠ 1 or Q5 ≠ 1) then Utility = Utility - **0.081**
 if (Q1=3 or Q2=3 or Q3=3 or Q4=3 or Q5=3) then Utility = Utility - **0.269**
 End of the sequential algorithm

10.6. Hospital Anxiety and Depression Scale

Hospital Anxiety and Depression Scale (HADS)

Tick the box beside the reply that is closest to how you have been feeling in the past week.
 Don't take too long over you replies: your immediate is best.

D	A		D	A	
		I feel tense or 'wound up':			I feel as if I am slowed down:
	3	Most of the time	3		Nearly all the time
	2	A lot of the time	2		Very often
	1	From time to time, occasionally	1		Sometimes
	0	Not at all	0		Not at all
		I still enjoy the things I used to enjoy:			I get a sort of frightened feeling like 'butterflies' in the stomach:
	0	Definitely as much		0	Not at all
	1	Not quite so much		1	Occasionally
	2	Only a little		2	Quite Often
	3	Hardly at all		3	Very Often
		I get a sort of frightened feeling as if something awful is about to happen:			I have lost interest in my appearance:
	3	Very definitely and quite badly	3		Definitely
	2	Yes, but not too badly	2		I don't take as much care as I should
	1	A little, but it doesn't worry me	1		I may not take quite as much care
	0	Not at all	0		I take just as much care as ever
		I can laugh and see the funny side of things:			I feel restless as I have to be on the move:
	0	As much as I always could		3	Very much indeed
	1	Not quite so much now		2	Quite a lot
	2	Definitely not so much now		1	Not very much
	3	Not at all		0	Not at all
		Worrying thoughts go through my mind:			I look forward with enjoyment to things:
	3	A great deal of the time	0		As much as I ever did
	2	A lot of the time	1		Rather less than I used to
	1	From time to time, but not too often	2		Definitely less than I used to
	0	Only occasionally	3		Hardly at all
		I feel cheerful:			I get sudden feelings of panic:
	3	Not at all		3	Very often indeed
	2	Not often		2	Quite often
	1	Sometimes		1	Not very often
	0	Most of the time		0	Not at all
		I can sit at ease and feel relaxed:			I can enjoy a good book or radio or TV program:
	0	Definitely	0		Often
	1	Usually	1		Sometimes
	2	Not Often	2		Not often
	3	Not at all	3		Very seldom

Please check you have answered all the questions

Note: Questions with response scoring under column header D are depression related questions. Otherwise, those are anxiety related questions.

10.7. Detailed Description of the Multiple Imputation Procedure

The following is a detailed description of the multiple imputation procedure which will be used for analysis of the secondary efficacy endpoints.

In general, the missing pattern is anticipated to be not monotone, a two-step approach will be used:

- Step 1: the MCMC method will be used in conjunction with the IMPUTE=MONOTONE option to create an imputed data set with a monotone missing pattern. Set the SEED=1629 option in SAS MI procedure.
- Step 2: Using the monotone data set from step 1, missing data will be imputed using the regression method. Set the SEED=9261 option in SAS MI procedure.

The imputation model for step 1 will include the treatment group and the values of the analyzed parameter at baseline and planned time-points up to week 24.

The imputation model for step 2 will include the same variables as in step 1 with the following additional variables:

- the randomization strata (apheresis treatment status strata);
- age, BMI, and gender (age and BMI included as continuous variables).

Non-continuous variables included in the imputer's model (i.e., treatment group, randomization strata and gender) are not expected to be missing.

In addition, for continuous efficacy variables anticipated to have a non-normal distribution (i.e. TG and Lp(a)), data will be log-transformed before imputation process and then back-transformed to create the imputed data sets using the TRANSFORM statement of SAS MI procedure.

For variables other than those continuous efficacy variables anticipated to have a non-normal distribution (i.e. TG and Lp(a)), for each simulation leading to negative imputed value, another value will be redrawn using MINIMUM option of SAS MI procedure.

The number of imputations (100) will be informally verified by replicating sets of 100 imputations and checking whether the combined results are stable. If not stable, the number of imputations will be increased and informally checked as above, and thus continued until stable estimates are obtained.

